2.2.2. Secondary Efficacy Endpoints

The secondary endpoints are as follows:

- Mean change from baseline in bilirubin (excluding patients with Gilbert's Syndrome) at the treatment assessment endpoint (mean of values at Weeks 23, 25, and 26)
- Mean change from baseline in QOL, as assessed by the change in Functional Assessment of Chronic Illness Therapy (FACIT)-Fatigue scale scores at the treatment assessment endpoint
- Mean change from baseline in lactate dehydrogenase (LDH) at the treatment assessment endpoint
- Number of transfusions and number of units after the first 5 weeks of study drug administration
- Mean change from baseline in Hgb at the treatment assessment endpoint

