3.1.2. Treatment

Eligible patients will receive an IV infusion of BIVV009 over approximately 60 minutes on Day 0, Day 7, and every 14 days thereafter through Week 25 (i.e., Days 21, 35, 49, 63, 77, 91, 105, 119, 133, 147, 161, and 175). Patients who weigh less than 75 kg will receive fixed doses of 6.5 g of BIVV009. Patients who weigh 75 kg or more will receive fixed doses of 7.5 g of BIVV009. Patients who miss a dose (i.e., outside the dosing window or > 17 days since last dose) should return to the site for an unscheduled visit 1 week prior to the next scheduled dose in order to receive an additional loading dose. Patients will have an EOT visit on Day 182 (Week 26).

During the 6-month treatment period, patients will receive a transfusion if his or her Hgb level meets either of the following criteria:

- Hgb is < 9 g/dL and the patient is symptomatic, or
- Hgb is < 7 g/dL and the patient is asymptomatic.

Following completion of dosing in the 6-month treatment period, patients will continue to receive BIVV009 dosing during Part B, the long-term safety and durability of response extension phase. Part B will run for approximately one year following last patient out (LPO) under Part A.

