5.1.1. Definitions

Study Day

Study Day is defined as days relative to the date of first dose of BIVV009, Day 0. In other words, Study Day 1 is Day 0 as defined in the protocol. The start/stop day of events will be calculated as (date of event – date of Study Day 1 + 1) if the date of event is on or after the first dose date, or (date of event – date of Study Day 1) if the date of event is before the first dose date.

Incomplete dates will be imputed for the calculation of study days, unless specified otherwise:

- If missing day only, the start date will be imputed as the first day of the month, while the end date will be imputed as the last day of the month;
- If missing day and month, the start date will be imputed as the first day of the year, while the end date will be imputed as the last day of the year;

Baseline

Baseline measures are defined as the last value prior to the administration of the study drug. If a transfusion occurs during the screening period, the baseline measure must be at least 7 days after the transfusion.

Part A Study Treatment Period

The Part A study treatment period starts at the date of first study drug administration and ends at the date of Week 26 visit if the subject completes Part A study treatment, or at the date of Early Termination (ET)/Safety Follow-up Visit if the subject discontinues the study treatment prior to Week 25.

Visit Windows

Analysis by study visit will utilize the data recorded on the corresponding nominal visit from electronic Case Report Forms (eCRFs). In case of missing data/assessments for a visit, data from an unscheduled visit, or EOT/ET/Safety Follow-up Visit will be used, if the Study Day of such a visit fits in the analytic window defined in [Table 1](#). If multiple values are identified within the analytic window, the one closest to the target study day will be used.

Table 1: Analytic Visit Windows

Visit	Target Study Day	Analytic Visit Window (Study Day)
Baseline (Day 0)	1	≤ 1
Week 1 (Day 7)	8	2 – 15
Week 3 (Day 21)	22	16 – 29
Week 5 (Day 35)	36	30 – 43
Week 7 (Day 49)	50	44 – 57
Week 9 (Day 63)	64	58 – 71
Week 11 (Day 77)	78	72 – 85
Week 13 (Day 91)	92	86 – 99
Week 15 (Day 105)	106	100 – 113
Week 17 (Day 119)	120	114 – 127
Week 19 (Day 133)	134	128 – 141
Week 21 (Day 147)	148	142 – 155
Week 23 (Day 161)	162	156 – 169
Week 25 (Day 175)	176	170 – 179
Week 26 (Day 182; EOT Visit in Part A)	183	180 – 189

Treatment Assessment Timepoint

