For either estimand, the mean change from baseline in LDH at treatment assessment timepoint, along with its 95% CI, will be estimated by the MMRM model ([Section 5.1.4.1](#)).

Additional sensitivity analyses for hypothetical estimand, similar to those specified for bilirubin, will be performed for the change from baseline in LDH at treatment assessment timepoint.

Additional descriptive analyses will be performed for LDH isoforms.

7.3.4. Number of Transfusions and Number of Units after the First 5 Weeks of Study Drug Administration

The number of transfusions after Week 5 through Week 26 visits will be summarized for the FAS, where the observed data will be used for subjects who discontinue study treatment early in Part A. The number of units transfused during the same period of time will be summarized for subjects who receive at least 1 transfusion.

The transfusions occurring during the first 5 weeks will be listed.

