7.3.1. Continuous Endpoints

The continuous endpoints include:

- Hemoglobin
- Bilirubin (total)

The above endpoints will be summarized by visit, starting at Baseline/Day 0 and will continue through the Week 77 visit. Summary tables will include change from baseline and individual summary statistics will follow those presented in [Section 5.2.1](#). For patients with more than 12 months of follow-up in Part B, all endpoints at the Week 79 visit and beyond will be provided in a data listing.

Line plots of mean hemoglobin and bilirubin over time, starting at Baseline/Day 0, will be presented. Additionally, a line plot of mean change from baseline in hemoglobin over time, starting at Baseline/Day 0, will be presented.

Additionally, the following continuous endpoints will be summarized by Study Period using FAS as specified in [Section 5.2.1](#):

- Number of transfusions and total transfusion units
- Annualized number of transfusions and annualized transfusion units

For number of transfusions and total transfusion units, data up to Week 77 will be considered, for both Part B and Combined Study Period summaries. All data after Week 77 will be provided in the listing.

For annualized number of transfusions and annualized transfusion units, all Part B data will be considered. Annualized values will be calculated for each patient using the following formula:

$$\text{Annualized value} = \frac{\text{Number of events during the Study Period}}{\text{Total number of days during the Study Period}} \times 365.25$$

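### The Part A transfusion endpoint summarises units only in transfused patients and counts transfusions without a follow-up denominator, so neither summary alone tracks transfusion need cleanly

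*SAP*

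**What the plan says.** The Part A SAP lists among its secondary efficacy endpoints (Section 2.2.2): "Number of transfusions and number of units after the first 5 weeks of study drug administration". Section 7.3.4 then uses two different populations.

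- Count: "The number of transfusions after Week 5 through Week 26 visits will be summarized for the FAS". Patients with no transfusion therefore enter as zeros. The rule for patients who stop early is given as "where the observed data will be used for subjects who discontinue study treatment early in Part A". No patient-time denominator, rate or imputation is given.
- Units: these "will be summarized for subjects who receive at least 1 transfusion". Patients with no transfusion are left out.

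The window for a completer runs from Week 5 (Day 35) to the Week 26 visit (Day 182). For an early discontinuer, Section 5.1.1 ends the Part A period "or at the date of Early Termination (ET)/Safety Follow-up Visit if the subject discontinues the study treatment prior to Week 25". Protocol Section 6.1.7 places that visit 9 weeks after the last dose and has transfusions recorded there. Section 7.3.4 does not say whether those transfusions count.

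Both remedies already exist in the sponsor's plans. Part A SAP Section 7.4.1.2.2 divides thromboembolic events by subject-years from Week 5. Part B SAP Section 7.3.1 summarises transfusions and units in its own FAS and adds "Annualized number of transfusions and annualized transfusion units".

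**The concern.** There are two separate problems, one in each half of the endpoint.

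**Units.** Being transfused after Week 5 is an outcome that the drug is meant to prevent. If treatment frees the lighter users from transfusion, the summary is left with the heavier users, and its mean goes up even though less blood was used.

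**Count.** A patient who leaves early has less time in which to be transfused and so contributes fewer transfusions, whatever the underlying need. Leaving may also be related to failure. Protocol Section 4.1 withdraws patients who need other treatment for the disease, and Part A SAP Section 5.1.4 expects such need to arise mainly from lack of response or breakthrough. The primary endpoint guards against this by counting unknown response as non-response; Section 7.3.4 has no counterpart. The FAS also contains patients who leave before Week 5, and the section does not say whether they enter as zeros for a window they never reached.

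What is at stake is the reading of a listed secondary endpoint on transfusion need, not the primary result.

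**Working it through.** Section 7.3.4 states no figure to reproduce. The inputs from the documents are N = 20 (Part A SAP Section 3.3) and a window of 26 − 5 = 21 weeks. Units per patient, transfusion rates and dropout rates are not given, so all of these are assumptions shown as ranges.

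**1. Units among the transfused against units in the FAS**

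FAS mean = (number transfused × mean among transfused) / 20.

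- 8 transfused, mean 4: the plan shows 4.0; FAS mean 8 × 4 / 20 = 1.6.
- 4 transfused, mean 6: the plan shows 6.0; FAS mean 4 × 6 / 20 = 1.2.

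The second outcome is better (24 units instead of 32) but looks worse. The same happens if 6 light users (2 units each) and 2 heavy users become 1 light and 2 heavy:

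| Units per heavy user | Total units | Mean among transfused | FAS mean |
|---|---|---|---|
| 4 | 20 → 10 | 2.5 → 3.3 | 1.0 → 0.5 |
| 6 | 24 → 14 | 3.0 → 4.7 | 1.2 → 0.7 |
| 8 | 28 → 18 | 3.5 → 6.0 | 1.4 → 0.9 |

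**2. Count with early leavers at an unchanged rate**

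Assume that every patient has 3 transfusions per 21 weeks, or 1/7 per week. If k of 20 leave at Week w, patient-weeks = (20 − k) × 21 + k × (w − 5), and mean count = patient-weeks / 7 / 20. If transfusions up to the early termination visit count, replace w by w + 9 (Week 18 or 22).

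For k = 4 and w = 9: 16 × 21 + 4 × 4 = 352 patient-weeks, and 352 / 140 = 2.51 against 3.00. With the 9 extra weeks: 16 × 21 + 4 × 13 = 388, and 388 / 140 = 2.77.

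| Leavers | Week | Mean, observation ends on leaving | Mean, observed to early termination visit |
|---|---|---|---|
| 2 | 9 | 2.76 (−8%) | 2.89 (−4%) |
| 2 | 13 | 2.81 (−6%) | 2.94 (−2%) |
| 4 | 9 | 2.51 (−16%) | 2.77 (−8%) |
| 4 | 13 | 2.63 (−12%) | 2.89 (−4%) |
| 6 | 9 | 2.27 (−24%) | 2.66 (−11%) |
| 6 | 13 | 2.44 (−19%) | 2.83 (−6%) |

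Total transfusions over total patient-time is 1/7 per week, or 7.45 per patient-year at 52.18 weeks per year, in every row.

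**3. What a rate does not repair**

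If 4 leavers have twice the rate, the full-follow-up mean is (16 × 3 + 4 × 6) / 20 = 3.60. With observation ending on leaving, the count shows 2.63 (Week 9) or 2.86 (Week 13), a fall of 27% or 21%. The pooled rate is 7.79 or 8.10 per patient-year against 8.95 with full follow-up: closer, but still low.

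**4. Which rate to use**

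The Part B formula annualises each patient separately. One transfusion in a patient followed for 7 days after Week 5 gives 1 / 7 × 365.25 = 52 per year and adds 52 / 20 = 2.6 to a 20-patient mean. A patient who leaves before Week 5 has no time at risk, so the ratio is undefined. Pooling events and time across patients avoids both.

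**The case against.** The strongest reply is that the plan shows enough to prevent misreading. Counts and units share one table, and Section 5.2.1 reports n with every mean, so 6.0 would stand beside n = 4 and 4.0 beside n = 8. FAS mean units can be rebuilt as mean × n / N. Section 7.2.1 gives the proportion meeting each response criterion, which includes freedom from transfusion, and Section 7.4.1.3 analyses time to first transfusion by Kaplan-Meier with censoring. Stating how many were transfused and then how much they received is a normal two-part description. Much of this stands. It makes the matter one of clear reporting of an estimated endpoint. But the FAS mean of units is left for the reader to rebuild, and Kaplan-Meier covers only the first event.

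Three stronger readings are tempting and do not hold.

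- A reader might infer that the whole endpoint can worsen as the drug works, or that transfusion need in the treated population goes unmeasured. The count is taken in the FAS with zeros, so only the units half behaves this way.
- A reader might infer that Part A cannot be compared with Part B. Part B SAP Section 7.3.1 plans raw and annualised transfusions and units by study period, and Section 5.1.1 there defines a combined period covering Part A. The true limit is that the Part B FAS contains only patients who entered Part B, so Part A dropouts are missing from it.
- A reader might infer a very large dropout effect. Suppose the only transfused patients are four who need one transfusion every 4 weeks and leave at Week 9. The count is 4 × 1 / 20 = 0.20 instead of 4 × (21 / 4) / 20 = 1.05. That is an extreme assumption, and if observation runs to the early termination visit the figure is 4 × (13 / 4) / 20 = 0.65. Transfused patients are also not withdrawn for that reason (Protocol Section 4.1).

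**Conclusion.** The point holds within those limits. The units summary conditions on a post-baseline outcome, and its mean can move opposite to total use: 4.0 to 6.0 while the FAS mean falls from 1.6 to 1.2 in the illustration. The transfusion count falls with early discontinuation at an unchanged rate. Under the assumed rate, 4 of 20 leaving at Week 9 or 13 lowers it by 12 to 16%, or by 4 to 8% if transfusions up to the early termination visit count. If transfusions become more frequent off drug and are counted, the effect could shrink further or reverse.

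All these sizes rest on assumed data. A reader might also take this as a threat to the trial's main claim. It is not one: Part A SAP Section 7.1.1 tests only the primary hypothesis, and this endpoint is descriptive in a single-arm study. The change is worth making because it is specific and close to free.

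**What to change.** Amend Part A SAP Section 7.3.4 as follows.

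1. Summarise units in the FAS with zeros included. Keep the transfused-only summary as a supplement.
2. Add pooled rates of transfusions and of units: total events divided by total patient-time from Week 5 to the last Part A observation, as Section 7.4.1.2.2 does for thromboembolic events. Do not use the mean of the Part B per-patient annualised values.
3. Show the number of patients transfused and the follow-up time in the same table.
4. State that patients who leave before Week 5 contribute no time at risk, and whether transfusions up to the early termination visit count. The numerator and the patient-time must follow the same rule.
5. Note that the rate corrects for shorter follow-up but not for dropout related to transfusion need.

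The cost is SAP wording, one derived follow-up variable and a few extra rows in a planned table. No new data are needed.

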7.3.5. Mean Change from Baseline in Hgb at the Treatment Assessment Timepoint

The change from baseline in Hgb at the treatment assessment timepoint will be analyzed for the FAS. The primary analysis will be performed according to Hypothetical Estimand (defined in

[Section 5.1.3](#)), while a sensitivity analysis will be done via De-facto Estimand ([Section 5.1.3](#)). Additional details are found in [Table 7](#).

Table 7: Estimands for Change from Baseline in Hgb

	Hypothetical Estimand	De-facto Estimand
Population	FAS	FAS
Variable	Change from baseline at treatment assessment time point, where any value after transfusion and prohibited medication is considered missing	Change from baseline at treatment assessment time point
Treatment effect	Mean change from baseline, if transfusion or prohibited medications had not been available	Mean change from baseline, irrespective of transfusion or prohibited medication use

For either estimand, the mean change from baseline in Hgb at treatment assessment timepoint, along with its 95% CI, will be estimated by the MMRM model ([Section 5.1.4.1](#)).

Additional sensitivity analyses for hypothetical estimand, similar to those specified for bilirubin, will be performed for the change from baseline in Hgb at treatment assessment timepoint.

7.4. Exploratory Endpoints

7.4.1. Part A Exploratory Endpoints

The analysis of exploratory endpoints (listed in [Section 2.2.3](#)) will be based on Observed Estimand ([Section 5.1.3](#)). Additionally, summary of hemolytic parameters (Hgb, bilirubin, LDH, haptoglobin, and reticulocyte) over visit is added to the SAP to examine the time trend of the improvement. Unless specified below, the endpoints will be summarized by visit for continuous and categorical variables, and for time to event variables (e.g., time to obtain Hgb level of ≥ 12 g/dL) for the entire Part A.

7.4.1.1. Continuous Endpoints

The continuous endpoints include:

- Mean change from baseline in QOL, as assessed by the change in the five level EQ-5D-5L scores at the treatment assessment endpoint and by visit
- Mean change from baseline in QOL, as assessed by the change in the 12-item short form survey (SF-12®) at the end of treatment assessment endpoint and by visit
- Mean change from baseline in hemolytic parameters (Hgb, total bilirubin, LDH, haptoglobin, and absolute reticulocyte) by visit
- Mean change from baseline in FACIT-F by visit (see [Section 7.5.1](#))

The endpoints by visit will be summarized for FAS according to [Section 5.2.1](#).

7.4.1.2. Response Endpoints

The response endpoints include:

- Incidence of solicited symptomatic anemia at EOT
- Incidence of thromboembolic events after the first 5 weeks of study drug administration
- Proportion of subjects with Hgb level of ≥ 12 g/dL at the treatment assessment endpoint
- Proportion of subjects normalizing haptoglobin at the treatment assessment endpoint
- Proportion of subjects normalizing bilirubin at the treatment assessment endpoint
- Proportion of subjects normalizing LDH at the treatment assessment endpoint
- PGIC and change from baseline in PGIS to assess subject's perception of changes in CAD disease burden at last scheduled visit of Part A
- Incidence of disabling circulatory symptoms at last scheduled visit of Part A
- Proportion of subjects normalizing Hgb (≥ 12 g/dL) by visit
- Proportion of subjects achieving 2 g/dL increase in Hgb by visit
- Proportion of subjects normalizing bilirubin by visit
- Proportion of subjects normalizing LDH by visit
- Proportion of subjects normalizing haptoglobin by visit

The endpoints will be summarized for FAS according to [Section 5.2.2](#).

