4.3.2 Secondary efficacy endpoints (Part A)

- Mean change from baseline in bilirubin (excluding patients with Gilbert's Syndrome) at the treatment assessment endpoint (defined as the mean value of Weeks 23, 25, and 26)
- Mean change from baseline in QOL, as assessed by the change in Functional Assessment of Chronic Illness Therapy (FACIT)-Fatigue scale ([Section 10.3](#), Appendix C) scores at the treatment assessment endpoint
- Mean change from baseline in lactate dehydrogenase (LDH) at the treatment assessment endpoint

- Number of transfusions and number of units after the first 5 weeks of study drug administration
- Mean change from baseline in Hgb at the treatment assessment endpoint

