5.1 INCLUSION CRITERIA

All patients must meet all the following inclusion criteria to be enrolled:

1. Adult males and female patients ≥ 18 years of age at Screening.
2. Body weight of ≥ 39 kg at Screening.
3. Confirmed diagnosis of primary CAgD based on the following criteria:
 - a) Chronic hemolysis
 - b) Polyspecific direct antiglobulin test (DAT) positive
 - c) Monospecific DAT strongly positive for C3d
 - d) Cold agglutinin titer ≥ 64 at 4°C
 - e) IgG DAT $\leq 1+$, and
 - f) No overt malignant disease
4. History of at least one documented blood transfusion within 6 months of enrollment.
5. Hemoglobin level ≤ 10.0 g/dL.
6. Bilirubin level above the normal reference range, including patients with Gilbert's Syndrome
7. Ferritin levels above the lower limit of normal. Concurrent treatment with iron supplementation is permitted if the patient has been on a stable dose during the previous 4 weeks.
8. Presence of one or more of the following CAgD-related signs or symptoms within 3 months of Screening:
 - a) Symptomatic anemia defined as:
 - i. Fatigue
 - ii. Weakness
 - iii. Shortness of breath
 - iv. Palpitations, fast heart beat
 - v. Light headedness, and/or
 - vi. Chest pain
 - b) Acrocyanosis

- c) Raynaud's syndrome
 - d) Hemoglobinuria
 - e) Disabling circulatory symptoms, and/or
 - f) Major adverse vascular event (including thrombosis)
9. Bone marrow biopsy within 6 months of Screening with no overt evidence of lymphoproliferative disease or other hematological malignancy. An additional bone marrow biopsy will be required if the prior bone marrow is deemed unsuitable for analysis by the Sponsor.
 10. Documented vaccinations against encapsulated bacterial pathogens (*Neisseria meningitidis*, including serogroup B *meningococcus* where available, *Haemophilus influenzae*, and *Streptococcus pneumoniae*) within 5 years of enrollment or as specified in [Section 6.1.1.1](#).
 11. Adequate IV access.
 12. If female, must be post-menopausal, surgically sterile, or be established on (≥ 3 months prior to Screening) and agree to continue to use the same highly effective methods of birth control throughout the study and for 9 weeks following administration of the last dose of study drug.
 13. Males must be surgically sterile for at least 90 days or when sexually-active with female partners of child-bearing potential will agree to use highly effective contraception from Day 0 until 9 weeks following administration of the last dose of study drug.

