7.3. Secondary Endpoints

7.3.1. Mean Change from Baseline in Bilirubin at the Treatment Assessment Timepoint

The change from baseline in bilirubin at the treatment assessment timepoint will be analyzed for FAS excluding subjects with Gilbert's syndrome. Gilbert's syndrome status is determined by the result of the genetic test at screening. If the result of Gilbert's syndrome test is not available for a patient, the patient will be excluded from the analysis. The primary analysis will be performed according to Hypothetical Estimand (defined in [Section 5.1.3](#)), while a sensitivity analysis will be done via De-facto Estimand ([Section 5.1.3](#)). Additional details are found in [Table 4](#).

Table 4: Estimands for Change from Baseline in Bilirubin

	Hypothetical Estimand	De-facto Estimand
Population	FAS excluding subjects with Gilbert's syndrome	FAS excluding subjects with Gilbert's syndrome
Variable	Change from baseline at treatment assessment time point, where any value after transfusion and prohibited medication is considered missing	Change from baseline at treatment assessment time point
Treatment effect	Mean change from baseline, if transfusion or prohibited medications had not been available	Mean change from baseline, irrespective of transfusion or prohibited medication use

For either estimand, the mean change from baseline in bilirubin at treatment assessment timepoint, along with its 95% CI, will be estimated by the MMRM model ([Section 5.1.4.1](#)).

If the number of subjects with unknown Gilbert's syndrome status is greater than 2, additional sensitivity analysis will be performed to include such subjects (unknown Gilbert's syndrome), whose baseline total bilirubin level is low to be considered less indicative of Gilbert's syndrome.

Additional sensitivity analysis based on multiple imputation ([Section 5.1.4.2](#)) will be carried out for the Hypothetical Estimand, utilizing the regression method with monotone missing patterns. Specifically, the following 4 imputation models will be considered:

- Change from baseline in bilirubin at treatment assessment timepoint is modeled as a function of baseline bilirubin value, weight stratum (< 75 kg, >= 75 kg), and bilirubin values from Day 7 through visits Week 21, visits prior to first transfusion, or visits prior to first prohibited medication use, whichever occurs first;

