Part A: Summary of change from baseline in hemoglobin (g/dL) at treatment assessment timepoint - De-facto estimand - MMRM
Part A: Summary of change from baseline in hemoglobin (g/dL) at treatment assessment timepoint - Hypothetical estimand – MI

[figure not shown]
Part A: Summary of change from baseline in bilirubin (umol/L) at treatment assessment timepoint (excluding subjects with Gilbert's syndrome) - Hypothetical estimand - MMRM
Part A: Summary of change from baseline in bilirubin (umol/L) at treatment assessment timepoint (excluding subjects with Gilbert's syndrome) - De-facto estimand - MMRM
Part A: Summary of change from baseline in bilirubin (umol/L) at treatment assessment timepoint (excluding subjects with Gilbert's syndrome) - Hypothetical estimand - MI
Part A: Summary of change from baseline in lactate dehydrogenase (U/L) at treatment assessment timepoint - Hypothetical estimand - MMRM
Part A: Summary of change from baseline in lactate dehydrogenase (U/L) at treatment assessment timepoint - De-facto estimand - MMRM
Part A: Summary of change from baseline in lactate dehydrogenase (U/L) at treatment assessment timepoint - Hypothetical estimand - MI
Part A: Summary of change from baseline in FACIT-Fatigue score at treatment assessment timepoint - Hypothetical estimand - MMRM
Part A: Summary of change from baseline in FACIT-Fatigue score at treatment assessment timepoint - De-facto estimand - MMRM
Part A: Summary of change from baseline in FACIT-Fatigue score at treatment assessment timepoint - Hypothetical estimand - MI
Part A: Summary of number of transfusions and units after the first 5 weeks of study drug administration
Efficacy: Exploratory - Hemolytic Parameters
Part A: Summary of change from baseline in hemoglobin (g/dL) by visit - Observed
Part A: Summary of change from baseline in bilirubin (umol/L) by visit - Observed
Part A: Summary of change from baseline in lactate dehydrogenase (U/L) by visit - Observed
Part A: Summary of change from baseline in haptoglobin (g/L) by visit - Observed
Part A: Summary of change from baseline in absolute reticulocyte ($10^9/L$) by visit - Observed
Part A: Plot of mean hemoglobin (g/dL) (+/- SE) by visit - Observed
Part A: Plot of mean change from baseline in hemoglobin (g/dL) (+/- SE) by visit - Observed
Part A: Plot of mean bilirubin (umol/L) (+/- SE) by visit (excluding subjects with Gilbert's syndrome) - Observed

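### SAP Part A excludes patients with Gilbert's syndrome from some bilirubin efficacy outputs and keeps them in others, without explanation, so the outputs are not comparable.

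*SAP*

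**What the plan says.** Protocol 5.1, inclusion criterion 6, admits these patients: "Bilirubin level above the normal reference range, including patients with Gilbert's Syndrome". The UGT1A1 test is done at screening, so status should normally be known.

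Protocol 4.3.2 defines the secondary endpoint as "Mean change from baseline in bilirubin (excluding patients with Gilbert's Syndrome) at the treatment assessment endpoint". SAP Part A 7.3.1 follows it: "The change from baseline in bilirubin at the treatment assessment timepoint will be analyzed for FAS excluding subjects with Gilbert's syndrome". It adds a rule for unknown status: "If the result of Gilbert's syndrome test is not available for a patient, the patient will be excluded from the analysis". If more than two patients have unknown status, a sensitivity analysis brings back those "whose baseline total bilirubin level is low to be considered less indicative of Gilbert's syndrome".

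The other bilirubin efficacy outputs are handled differently:

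- SAP 5.1.1 defines normalisation as total bilirubin no higher than the central laboratory's upper limit of normal (ULN). It has no Gilbert's rule.
- SAP 7.4.1.2 lists "Proportion of subjects normalizing bilirubin at the treatment assessment endpoint", and the same proportion by visit, and assigns both to the FAS.
- SAP 7.4.1.1 (mean change by visit) and 7.4.1.3 (time to first normalisation) also name the FAS.
- In the SAP section 12 output list, the by-visit table is titled "Part A: Summary of change from baseline in bilirubin (umol/L) by visit - Observed", with no exclusion. The by-visit plots of mean bilirubin and of mean change in bilirubin both carry the Gilbert's exclusion in their titles.

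**The concern.** One laboratory parameter is reported in at least two populations, and nothing tells the reader why. The clearest case is the by-visit mean change, where the table includes Gilbert's patients and its companion plot leaves them out.

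The normalisation outputs raise a question of interpretation. Suppose Gilbert's syndrome adds a roughly constant amount to bilirubin for a reason other than haemolysis. That amount largely cancels in a change from baseline, but it does not cancel against a fixed ULN. On that supposition the exclusion is applied to the less exposed measure and omitted from the more exposed one. Patients who rarely reach ULN would stay in the denominator of the proportion and in the risk set of the time-to-event curve. A reader who sets the mean change beside the normalisation rate would be comparing different groups of patients.

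**Working it through.** **Plan's own figures.** The documents give no number for Gilbert's patients and none for bilirubin normalisation. The only design figure concerns the primary endpoint: 20 patients, true rate 66%, at least 11 responders, 90% probability of success. The exact binomial calculation gives 89.7%, so the figure reproduces. It does not depend on bilirubin.

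**Populations side by side (SAP Part A).**

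| Output | Source | Gilbert's patients |
|---|---|---|
| Secondary mean change | 7.3.1 and its section 12 tables | Excluded, with unknown status |
| By-visit plots, mean and mean change | Section 12 | Excluded; title silent on unknown status |
| By-visit change table | 7.4.1.1, section 12 | Included |
| Proportion normalising, at endpoint and by visit | 7.4.1.2, section 12 | Included |
| Time to first normalisation | 7.4.1.3, section 12 | Included |

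The Observed Estimand (5.1.3), which governs the exploratory endpoints, restricts the FAS by retention and available data, not by Gilbert's status. It therefore does not supply the missing exclusion.

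**Effect on the normalisation rate.** Let N be the patients observed, g those with Gilbert's syndrome, q the normalisation rate without the syndrome and h the rate with it.

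- FAS rate = [(N − g)q + g·h] / N
- Shortfall against q = g(q − h) / N

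The values of g, q and h are all assumed, as is N = 20 with nobody missing.

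- Simple illustration with 12 normalising and h = 0: 12/20 = 60% in the FAS, 12/18 = 66.7% if g = 2, 12/16 = 75% if g = 4.
- With q = 70% and h = 0, each Gilbert's patient costs 0.70/20 = 3.5 points. The FAS rate is 63% at g = 2 and 56% at g = 4.
- Over g = 1 to 5 and q = 50% to 90%, the shortfall is 2.5 to 22.5 points if h = 0, and 0 to 10 points if h = 50%.
- If g = 0 the shortfall is zero.

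**Effect on time to normalisation.** With no censoring and h = 0, the median is reached only if the share of non-Gilbert patients who normalise is at least 0.5 × 20/(20 − g). That is 50% at g = 0, 55.6% at g = 2 and 62.5% at g = 4.

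**Part B.** SAP Part B 7.3 and 7.3.1 assign total bilirubin to the FAS, while the Part B output titles for the same table and plot exclude Gilbert's patients. There the text and the titles disagree.

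**The case against.** The split begins in the protocol. Section 4.3.2 attaches the exclusion to the secondary mean change, and 4.3.3 lists bilirubin normalisation and time to normalisation without it. SAP 2.2.2 and 2.2.3 repeat this. For those endpoints the SAP follows the protocol, and narrowing their population is partly a matter of preference. This stands. The firmest inconsistency is the by-visit table against the plot.

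A reader might infer that the FAS normalisation rate is biased. The documents do not support that: the planned quantity is the proportion of observed FAS patients at or below ULN, and as a description of the treated patients it is sound. The difficulty arises only when it is read as a measure of haemolysis control or set beside the mean change.

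A reader might also infer that the SAP excludes these patients because their bilirubin is raised for reasons unrelated to haemolysis, or that they cannot normalise. SAP 7.3.1 gives no reason. Its nearest statement only treats a low baseline value as less suggestive of the syndrome. The rest is assumption.

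The consequences are limited. The endpoints are exploratory and SAP 7.1.1 tests no formal hypothesis beyond the primary. Gilbert's test results are to be summarised and efficacy data listed, so a reader with the listings could recompute. Finally, applying the 7.3.1 rule drops patients of unknown status, who may not have the syndrome, from a sample of about 20. That is a reason to keep the FAS result as well.

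**Conclusion.** The inconsistency of populations holds and is not reconciled anywhere in the documents. It concerns comparability and interpretation and is minor. The by-visit table and plot can differ, but only if at least one Gilbert's patient contributes data; it does not follow that they will.

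The understatement of haemolysis control rests on one assumption that the documents do not state, namely that Gilbert's patients reach ULN less often than others. If so, the direction is against the drug. The illustrative 60% against 67% to 75% also assumes 20 observed patients, 12 normalisers, 2 to 4 Gilbert's patients and no normalisation among them. The true gap cannot be found from the documents and may be zero.

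**What to change.** In SAP Part A 7.4.1.1 to 7.4.1.3 and the output list, present the by-visit bilirubin table, the proportion normalising bilirubin and the time to bilirubin normalisation for the FAS without Gilbert's patients, using the 7.3.1 rule including its treatment of unknown status. Keep the full-FAS result for each as a supplementary summary. List the excluded patients with their reason, genotype or unknown status. Make the table and plot titles match, and align the Part B text with its output titles in the same way.

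The cost is small: a short SAP change, a few more outputs and a slightly smaller denominator. No new data are needed, because the UGT1A1 result is already collected.
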